### **Disease progression**

Disease progression can be considered as a worsening of a patient's condition attributable to the disease for which the investigational product is being studied. It may be an increase in the severity of the disease under study and/or increases in the symptoms of the disease. The development of new, or progression of existing metastasis to the primary cancer under study should be considered as disease progression and not an AE. Events that are unequivocally due to disease progression should not be reported as AEs during the study.

### **New Cancers**

The development of a new cancer should be regarded as an AE and will generally meet at least one of the serious criteria. New cancers are those that are not the primary reason for the administration of the study treatment and have been identified after the patient's inclusion in this study. They do not include metastases of the original cancer.

### **COVID-19 Infections**

COVID-19 infections occurring from main study ICF until 30 days after discontinuation of study treatment should be reported as adverse events. Patients who test positive for COVID-19, but do not have any symptoms should be reported as ‘asymptomatic COVID-19’. If COVID-19 is suspected but not confirmed by a diagnostic test, then ‘suspected COVID-19’ should be reported. The AE term for the ‘suspected COVID-19’ should be updated when the results of the diagnostic test are known to reflect the confirmed COVID-19 or alternative diagnosis (e.g. common cold, influenza etc).

### **Taste Disturbances**

Loss or altered taste (dysgeusia) is an on-target AE known to occur with porcupine inhibition (Ref 30, Ref 18). According to CTCAE v5, there are only two grades of dysgeusia:

Grade 1 - Altered taste but no change in diet

Grade 2 - Altered taste with change in diet (e.g. oral supplements); noxious or unpleasant taste; loss of taste.

As dysgeusia is poorly characterised by CTCAE grade alone, site research personnel will complete a taste assessment (consisting of a specific set of questions and an oral examination) at screening for each patient enrolled in Module 3, and for any patient in Module 3 who reports dysgeusia in response to the open question from the study site staff;

*‘Have you had any health problems since the previous visit/you were last asked?’*

In such cases, the assessment will be performed at each visit until the AE has resolved. The information will be recorded and analysed as part of the overall safety objective of the study.

## **4.2 Reporting of Adverse Events, Serious Adverse Events and Dose Limiting Toxicities**

TEAEs reported during the study will be coded using a Medical Dictionary for Regulatory Activities (MedDRA) dictionary. Incidence of treatment-emergent adverse events will be summarised by disease and cohort and the following:

- System organ class and preferred term
- System organ class, preferred term and severity

These summaries will be presented for the following subsets:

- SAEs
- All AEs
- Drug-related AEs
- AEs leading to treatment discontinuation

For tables reporting AEs by severity, if a patient has multiple occurrences of an AE with the same organ class and preferred term, the most severe event will be presented.

All SAEs will be recorded on the SAE Report form, the Adverse Events form in the CRF, and source documents. Criteria for documenting the relationship to study drug as well as severity and outcome will be the same as those previously described.

All SAEs that are spontaneously reported within 30 days of a patient's last dose of RXC004 (for Module 1) or 90 days of a patient's last dose of nivolumab (for Module 2) are to be collected and reported as previously described.

The original CRF pages should be returned immediately to the CRF binder. The information must include at least the following:

- Name, address and telephone number of the reporting Investigator.
- Investigational product and study code.
- Patient identification number, sex and age at study entry.
- Description of the AE, measures taken and outcome.
- Preliminary classification of causal relationship by the Investigator.

The Principal Investigator (or designee) will notify IQVIA within 24 hours of identifying a DLT or SAE, whether related or unrelated to investigational drug, see Section 3.

Additional follow-up information should be completed on an SAE follow-up form with a copy sent to the Sponsor or IQVIA and the original placed in the SAE section of the CRF binder.

#### **4.2.1 Reporting of SAEs and Suspected Unexpected Serious AEs to Regulatory Authorities, Ethics Committees and Investigators**

In accordance with the European Commission Clinical Trials Directive (2001/20/EC), the delegated CRO is responsible for submitting reports of AEs associated with the use of the drug that are both serious and unexpected to the regulatory authorities and Independent Ethics Committees / Institution Review Boards (IEC/ IRB) according to local laws and regulations. All investigators participating in clinical studies with the study medication will receive copies of these reports - Council for International Organisations of Medical Sciences (CIOMS) for prompt submission to their local institution / regulatory bodies. Other SAEs (i.e. expected or unrelated SAEs) should be reported per the relevant institution's procedures. Investigators should provide written documentation of notification for each report to IQVIA.

Until such time that an AE is included in the IB reference safety information, it should be considered unexpected, regardless of whether the AE has been the subject of a previous Safety Update. All expectedness assessments will be made by the Sponsor or designee.

Suspected Unexpected Serious Adverse Reactions (SUSARs) are required to be reported within 7 calendar days for life-threatening events and those resulting in death, or 15 calendar days for all others. These timeframes begin with the first notification of the SUSAR to IQVIA or Redx from the Investigator.

#### **4.2.2 Follow-Up of Adverse Events**

Any AEs observed from the time of consent/randomisation up to the end of the study will be followed up to resolution. Resolution means that the patient has returned to a baseline state of health or the Investigator does not expect any further improvement or worsening of the AE. All AEs that occur after the patient completed a clinical study should also be reported to IQVIA Clinical within 30 days of the last dose of study drug.

### **4.3 Medical Emergencies and Sponsor Contacts**

#### **4.3.1 Safety Reporting and Medical Management**

Following the completion of each dose-escalation cohort of Modules 1 and 2, the SRC will meet to evaluate the safety and tolerability and, where available, PK of RXC004 to decide the next dose and/or schedule as previously discussed in SRC Section 3.2. Dose interruptions and reductions will be taken into account. AEs occurring in Cycle 2 and beyond which meet the definition of a DLT or are considered clinically significant may also be considered in making dose escalation decisions. Other AEs, or possible trends in AEs, during the dose escalation phase may inform on dose escalation.

### **4.3.3 Overdose**

Investigators should be advised that any patient who receives a higher dose than that intended should be monitored closely, managed with appropriate supportive care and followed up expectantly. There are no data regarding RXC004 overdose in humans. An overdose and AEs should be treated per standard medical practice.

Dosing details should be captured in the CRF. If the patient receives a dose of a study drug that exceeds protocol specifications and the patient is symptomatic, then the symptom(s) should be documented as AEs in the CRF and, if serious, submitted to the Sponsor's designated safety contact on an SAE Report Form. Do not record the overdose as an AE if the patient is not symptomatic.

### **4.3.4 Pregnancy**

A Pregnancy Report Form (or equivalent) must be completed for all pregnancies that occur from the time of first study drug dose until 6 months after the last dose of study drug(s) received, including any pregnancies that occur in the female partner of a male study patient. Additionally, all pregnancies should be reported that occur in a male patient's partner if the estimated date of conception occurred after the male patient's first dose of study drug. The form must be transmitted to the Drug Safety Department of IQVIA within 48 hours of becoming aware of the pregnancy. All pregnancies will be monitored for the full duration; all perinatal and neonatal outcomes should be reported. Infants should be followed for a minimum of 8 weeks after their delivery.

Collection of data on the CRF: All pregnancies (as described above) that occur within 30 days of the last dose of study drug(s) will also be recorded as an AE. Abortion (whether spontaneous, therapeutic, or planned) should be reported as an SAE. Congenital anomalies or birth defects should be reported as SAEs.

## 5 STUDY DESIGN

### 5.1 Introduction

The study is a modular Phase 1, dose-escalation, open-label study to assess the safety, tolerability, PK and preliminary anti-tumour activity of RXC004 in monotherapy and in combination in patients with advanced malignancies.

The study started with the RXC004 monotherapy module (Module 1, a monotherapy dose escalation to identify the minimum biologically active dose (MBAD), maximum tolerated dose (MTD) or maximum feasible dose (MFD), in multiple patient cohorts. Module 2 was added with protocol amendment v5, a RXC004 and nivolumab combination dose escalation to identify the MTD or MFD of RXC004 in combination with nivolumab.

Module 3 will determine whether RXC004 2 mg QD monotherapy intermittent schedules are safe/tolerated. This Module will initially start with two Arms – RXC004 2 mg QD taken for 4 days, followed by 3 days off, repeated weekly for 21-day cycles (Arm 1) and RXC004 2 mg QD taken for 2 weeks, followed by 1 week off (Arm 2). The option to start further modules will be the decision of the SRC, based on emerging pre-clinical data and, safety and tolerability information from the initial module. A substantial protocol amendment with relevant preclinical and clinical data will be put in place before starting any further modules.

The dose escalation and dose escalation cohort size and the stopping criteria for Modules 1 and 2 are based upon accepted methodologies for Phase 1 oncology studies. Module 3 has a single cohort for each intermittent schedule.

### 5.2 Module 1 – RXC004 Monotherapy

The reason for conducting this study module is to provide the first cancer patient safety and tolerability data with RXC004.

Treatment, conduct, and withdrawal, which include starting dose and the dose escalation scheme, can be found in Section 3.1.2

Module 1 will commence by enrolling patients with advanced solid tumours into a SAD/MAD monotherapy dose-escalation arm. Eligible participants will be enrolled in sequential cohorts treated with RXC004 given as an oral capsule dose while being monitored for safety and DLTs.

Dose levels will not be weight-adjusted and the starting dose for the study will be RXC004 0.5 mg QD on Days 1-21 inclusive (for Cycle 1 and subsequent cycles). Dose increments will be guided by safety data observed during Cycle 1, as well as on-going assessment of safety beyond

Cycle 1 in earlier cohorts, plus PK and pharmacodynamic data as available. Every new dose cohort will be evaluated for the occurrence of a DLT during Cycle 0 or Cycle 1 of treatment. Patients will receive a single dose of RXC004 (Cycle 0) followed by a washout period (6-10 days) before receiving 21 continuous days dosing of RXC004 capsules (refer to Figure 4).

Module 1 will evaluate the safety and tolerability of RXC004 as monotherapy to provide dose(s) and schedules(s) for further modules, each evaluating the safety and tolerability of a specific combination agent. Module 1 will also provide preliminary efficacy readouts.

## **5.2.1 Module 1: Study Objectives**

The study objectives are detailed in Section 1.9

## **5.2.2 Module 1 Eligibility Criteria**

### ***5.2.2.1 Module 1-Specific Inclusion Criteria***

There are no Module 1-specific inclusion criteria. Patients must fulfill all of the core inclusion criteria in order to be eligible to receive study treatment in Module 1. The core inclusion criteria are detailed in Section 2.1.1

### ***5.2.2.2 Module 1-Specific Exclusion Criteria***

There are no Module 1-specific exclusion criteria. Patients must not meet any of the core exclusion criteria in order to be eligible to receive study treatment in Module 1. The core exclusion criteria are detailed in Section 2.

### ***5.2.2.3 Restrictions***

Study restrictions are explained in Section 2.3 and prohibited concomitant treatments are explained in Section 2.3.1.

## **5.2.3 Ascending Monotherapy SAD/MAD**

Module 1 will commence with an accelerated dose-escalation schedule and enrol three patients into a cohort with follow-up for AEs and DLT.

Patients will receive a single dose of RXC004 on Day 1 followed by a 6-10 days' washout period (Cycle 0) [this washout period may change based upon emerging data]. Cycles of 21

[figure not shown]
days of multiple dosing will then begin until the patient is withdrawn from the study (Cycle 1 onwards).

Dose escalation will continue in a 3+3 design until MBAD (as defined in Section 3.1.5) has been found to be tolerated. Subsequent dose escalation will continue in a 3+3 design until MTD/MFD has been reached.

The decision to dose escalate will be made upon the assessment of the safety and tolerability data collected up until the time of study drug administration on Cycle 2, Day 1. This DLT assessment period was selected as any acute toxicities leading to cessation of dose escalation in this study are anticipated to present within this duration. Doses and/or schedules of RXC004 will be defined by the SRC.

Optional skin-punch biopsies will be taken from all patients in Module 1 at baseline and while receiving treatment for analysis of pharmacodynamic markers of Wnt pathway inhibition (see Schedule of Assessments in Appendix 1).

**Figure 4** Module 1 RXC004 monotherapy SAD/MAD

- SRC approval for next cohort escalation or expansion required.
- In this example schematic diagram MBAD is achieved following the completion of Cohort 1
- Single dose of RXC004 following by a washout period of 6-10 days (Cycle 0) then 21 days' continuous dosing (Cycle 1 onwards) until withdrawal.

In Module 1, MBAD will be defined using either PK or pharmacodynamic data.

### 5.2.4 Selection of Doses

In Module 1, the starting dose of RXC004 will be 0.5 mg given once daily on Days 1–21 inclusive.

The study will start with Module 1 (monotherapy), in which the selected RXC004 starting dose of 0.5 mg QD (for the multiple dosing schedule) will be used, based on the clinical PK observed in Patient 001/001, the cover required for tumour efficacy in pre-clinical studies and the exposure over IC50 achieved by competitor PORCN inhibitors in their reported Phase1 studies (see Section 3.1.1). Eligible participants will be enrolled in sequential cohorts treated with RXC004, given as an oral capsule dose while being monitored for safety and DLTs.

## **5.2.5 Selection and Timing of Dose for Each Patient**

The doses and duration of treatment for Module 1 is detailed in Section 5.2.3. The exact times the study drug was administered and comments are to be recorded directly on the appropriate page of the CRF.

### **5.2.5.1 Dose Regimen**

The pre-clinical toxicology data support continuous dosing of RXC004 in humans, and Module 1 will start with this schedule. However, based on emerging data, the SRC may decide to propose the exploration of intermittent schedules in some modules.

### **5.2.5.2 Dose-Escalation Plan**

A general description of the study dose-escalation scheme can be found in Section 3.1

The dose-escalation scheme will not exceed doubling of the dose, in principle. However, up to a quadrupling of the dose may be permitted in the first two escalations only, if the drug concentrations of the first or second level are immeasurable or below the predicted target drug exposure for biological effect (for example more than 2-fold) and there have been no significant safety or tolerability issues. This will ensure that the fewest possible cohorts are exposed to RXC004 below the presumed therapeutic dose. The planned dose escalation scheme has the flexibility to be amended in light of emerging data.

Redx will interpret the single dose PK data before continuous dosing commences. If exposure levels indicate that a continuous schedule is not appropriate the patient may be discontinued or referred to the SRC to whether an alternative dosing schedule should be considered.

Table 3 shows an indicative dose escalation scheme for Module 1. All dose levels beyond Cohort 1 may change in light of emerging safety, tolerability, and PK data, and also evolving relevant pre-clinical data.

**Table 3: Indicative Dose-Escalation Scheme for Module 1**

Planned Dose levels	Dose
1	0.5 mg QD
2	1.0 mg QD
3	1.5 mg QD
4	2.0 mg QD
5	2.5 mg QD
6	3.0 mg QD

Note: This indicative dose and schedule optimisation scheme subject to SRC recommendation.

The pre-clinical toxicology data support continuous dosing of RXC004 in humans, and Module 1 will start with this schedule. However, based on emerging data, the SRC may decide to propose the exploration of intermittent schedules in some modules.

Please see IB for further details.

### 5.2.6 Dose-Limiting Toxicity for Module 1 (RXC004 Monotherapy)

The DLT assessment period runs from the start of dosing with RXC004 (Cycle 0 Day 1) up to Cycle 1 Day 21 for patients enrolled in Module 1.

A DLT is defined as an AE or abnormal laboratory value that occurs from the first dose of study treatment up to Cycle 1 Day 21, assessed as unrelated to disease progression, intercurrent illness, or concomitant medications that despite optimal therapeutic intervention meets any of the following criteria:

1. Haematological toxicity that is:
  - CTCAE  $\geq$  Grade 4 present for more than 4 consecutive days
  - Grade 3 neutropenia (ANC  $\geq$  500 to  $<$  1000 cells/mm^3) of any duration accompanied by fever ( $\geq$  38.5°C) and/or systemic infection
  - Grade 3 thrombocytopenia (25,000 to  $<$  50,000/mm^3) with clinical evidence of bleeding
2. Any other confirmed haematological toxicity CTCAE  $\geq$  Grade 4 (a repeat may be required for confirmation of an isolated abnormality in the absence of clinical signs, symptoms or other abnormal investigations, i.e. a suspected spurious value)
3. Non-haematological toxicity CTCAE  $\geq$  Grade 3 including:

- Laboratory abnormalities that are considered clinically significant by the investigator (with or without clinical symptoms or signs)
  - QTc prolongation ( $> 500$  msec or 60 msec above baseline)
4. Any other toxicity that:
- Is greater than that at baseline, is clinically significant and/or unacceptable, and is judged to be a DLT by the SRC
  - Is a protocol defined stopping criterion and is suspected to be RXC004 related
  - Results in an interruption of dosing schedule of more than 14 days

A DLT excludes:

1. Inadequately treated  $\leq$ Grade 3 nausea and/or vomiting and  $\leq$ Grade 3 diarrhoea
2. Any toxicity clearly unrelated to RXC004 e.g. solely related to the disease or disease-related process under investigation
3. Isolated laboratory changes of any grade without clinical sequelae or clinical significance

The incidence and type of DLT-type toxicity emerging from treatment beyond Cycle 1 Day 21 will be taken into account by the SRC in determining dose-escalation steps.

### **5.2.7 RXC004 Monotherapy: Dose Modifications**

If a patient experiences a clinically significant and/or unacceptable event including a DLT not attributable to the disease or disease-related processes under investigation, RXC004 dosing may be interrupted or the dose reduced and supportive therapy administered as required.

If the event resolves or reverts to  $\leq$  CTCAE grade 2, treatment with RXC004 may be restarted using the rules below for dose modifications, only following agreement with the Sponsor Physician. Patients who are at the lowest possible dose, i.e., in Cohort 1 or who have their dose previously reduced to the Cohort 1 dose and who have demonstrated an acceptable response to the dose interruption may be permitted to restart at the lowest dose level at the discretion of the Investigator.

For all other events, if the event does not resolve to  $\leq$  CTCAE grade 2 or the patient is not showing clinical benefit, then the patient should be discontinued from treatment and observed until resolution of the event.

Maximum tolerated dose will be defined in the presence of optimal supportive care for the event in question.

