**Table 4 Module 1 Dose Interruption and Stopping Criteria**

Event	Action
Diarrhoea	Treat as per Diarrhoea/Colitis Management and Treatment Guidelines
1st incidence of diarrhoea $\geq$ grade 2 (suspected RXC004 related):	Please refer to Appendix 5 Temporarily interrupt RXC004 for up to 14 days*. Consider restarting at lower dose if resolved to $<$ grade 1
2nd occurrence of $\geq$ grade 2 diarrhoea	Temporarily interrupt RXC004 for up to 14 days*. Consider restarting at lower dose if resolved to $<$ grade 1
3rd occurrence of $\geq$ grade 2 diarrhoea	Permanently discontinue study treatment
Bone events	
Confirmed RXC004 related fragility bone fracture (excluding grade 1 vertebral deformities)	Permanently discontinue study treatment
Patients with a DXA scan showing $\geq$ 7% worsening in BMD at lumbar spine or total hip compared to baseline	Permanently discontinue study treatment
An individual increase in $\beta$ -CTX of $\geq$ 350pg/ml from the baseline (screening) value or in individual measurement of $\geq$ 1000pg/ml	Permanently discontinue study treatment unless the patient has received clinical benefit (investigator assessment) and continued treatment is warranted.
Hepatic events	
Grade 3 increases in ALT or AST or ALP ( $>$ 5 x ULN if baseline normal, $>$ 5 x baseline, if baseline abnormal)	Permanently discontinue study treatment
Grade 2 increases in ALT or AST or ALP ( $>$ 3 x ULN if baseline normal, $>$ 3 x baseline, if baseline abnormal) with the appearance of symptoms associated with a clinical diagnosis of hepatitis including right upper quadrant pain or tenderness, fever, rash or eosinophilia ( $>$ 5%)	Permanently discontinue study treatment

Event	Action
Grade 2 increases in ALT or AST (> 3 x ULN if baseline normal, >3 x baseline, if baseline abnormal) and total bilirubin > 2 x ULN or INR* > 1.5 or other evidence of impairment to the synthesis function of the liver]	Permanently discontinue study treatment
*Unless patient is receiving warfarin	
Other adverse events	
Grade 3-4 toxicity (1 st event ^ )	Interrupt RXC004 (max. 14 days*), resume at the next lowest dose level when resolved (grade ≤ 2 or returns to baseline).
Grade 3-4 toxicity (subsequent events ^ )	Permanently discontinue study treatment

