Grade < 3 toxicity (all events ^ )	Decision to interrupt RXC004 (max. 14 days*) is at the Investigator's discretion. Resume at same dose prior to interruption.
^ Excluding diarrhoea	
Surgery	Interrupt RXC004 (max. 14 days*), resume at full dose. RXC004 should be stopped 3 days prior to surgery and resumed approx. 10 days later. If the wound has not healed a further 7 days are permitted prior to re-starting RXC004 at the discretion of the Investigator and with approval of Sponsor Physician.  No stoppage is required for biopsy procedures.
Vomiting	If vomiting occurs shortly after RXC004 is swallowed, the dose may be replaced if all of the intact capsules can be counted. Resume with the following scheduled dose.
Missed dose	Allowed to take the scheduled dose up to 4 hours after the scheduled dose time. If greater than 4 hours, the missed dose should not be taken and patient should continue with next dose at allotted time.

Event	Action
Corticosteroid use	
Patients receiving corticosteroids for treatment of diarrhoea should hold RXC004 (for max. 14 days*) as per Diarrhoea/Colitis Management and Treatment Guidelines (please refer to Appendix 5)
 
Patients receiving corticosteroids for any indication other than diarrhoea, should continue RXC004 at current dose level.
 
Patients who require on-study oral or intravenous (i.v.) glucocorticoids for > 4weeks at daily doses equivalent to <math>\geq 7.5</math> mg of oral (p.o.) prednisolone (for any indication other than diarrhoea) should temporarily interrupt RXC004 (for a maximum of 14 days*) if receiving clinical benefit (in the opinion of the investigator) and resume at full RXC004 dose once the daily corticosteroid dose equivalent falls to <7.5 mg PO prednisolone.
 
RXC004 should be permanently discontinued for patients who require on-study oral or intravenous (i.v.) glucocorticoids for > 4weeks at daily doses equivalent to <math>\geq 7.5</math> mg of oral (p.o.) prednisolone and are not receiving clinical benefit from RXC004 (in the opinion of the investigator)

\* RXC004 interruptions of greater than 14 days may be allowed for patients judged by investigator to be clinically benefiting from study treatment, and only after consultation with Sponsor

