### 5.4.4 RXC004 Intermittent Schedules

Module 3 will enroll 6 evaluable patients per Arm, with follow up for PK, pharmacodynamics and AEs.

An evaluable patient in Module 3 is defined as a patient that has received study treatment and either:

- Has completed minimum safety evaluation requirements and has received 100% of the specified RXC004 dose in Cycle 0 and at least 80% of the intended dose of RXC004 during Cycles 1 and 2.

- Has permanently discontinued study treatment due to a related adverse event

Subjects will start with a single dose of RXC004 followed by a washout of 3-7 days (Cycle 0). RXC004 schedules will commence on Cycle 1, Day 1. Each treatment cycle will be 21 days. Study treatment will continue until disease progression, intolerable toxicity or withdrawal of consent. Module 3 will start with two treatment Arms of intermittent RXC004 schedules;

- Arm 1 – 2mg QD RXC004 for 4 days, followed by 3 days off, repeated weekly for 21 day treatment cycles
- Arm 2 – 2mg QD RXC004 for 2 weeks, followed by 1 week off (21 day treatment cycles)

Patient enrolment into Arms 1 and 2 will run concurrently.

Further RXC004 monotherapy arms may be opened after review of safety and tolerability information from Arms 1 and 2, relevant data from Modules 1 and 2 and any emerging preclinical data.

[figure not shown]
Mandatory skin punch biopsies will be taken from all patients in Module 3 at baseline and while receiving treatment for analysis of pharmacodynamic markers of Wnt pathway inhibition, alongside PK sampling (see Schedule of Assessments in Appendix 9).

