#### 5.4.6 RXC004 Dose Modifications

If a patient experiences a clinically significant and/or unacceptable event not attributable to the disease or disease-related processes under investigation, RXC004 dosing may be interrupted, the dose reduced and supportive therapy administered as required.

If the event resolves or reverts to CTCAE  $\leq$  Grade 2, treatment with RXC004 may be restarted using the rules below for dose modifications, only following agreement with the Sponsor physician.

If the event does not resolve to CTCAE  $\leq$  Grade 2, or the patient is not showing clinical benefit, then the patient should be discontinued from treatment and observed until resolution of the event.

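### Section 5.4.6 stops a patient who shows no clinical benefit, while Table 7 resumes after a resolved first Grade 3-4 event with no benefit condition; Section 5.2.7 and Table 4 disagree in the same way

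*Protocol*

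**What the plan says.** **Module 3 text (protocol 5.4.6).** Dosing may be interrupted or reduced for a clinically significant or unacceptable event that is not due to the disease. If the event settles to Grade 2 or lower, restart is possible, but only with the Sponsor physician's agreement. If it does not settle, "or the patient is not showing clinical benefit, then the patient should be discontinued from treatment".

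**Module 3 table (protocol 5.4.7, Table 7).** After a first related Grade 3-4 event, RXC004 is interrupted for at most 14 days and resumed one level down once the event is Grade 2 or lower or back to baseline. Clinical benefit and Sponsor consultation enter this row only through footnote b, for interruptions beyond 14 days.

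**Module 1 text (protocol 5.2.7).** After resolution, "treatment with RXC004 may be restarted using the rules below for dose modifications, only following agreement with the Sponsor Physician". The discontinuation sentence has the same two limbs as 5.4.6: if the event does not settle, or if "the patient is not showing clinical benefit, then the patient should be discontinued from treatment and observed until resolution of the event". Its opening, however, limits it to all other events without saying which those are. A separate sentence covers Cohort 1 patients and patients already reduced to the Cohort 1 dose. If they responded acceptably to the interruption, they "may be permitted to restart at the lowest dose level at the discretion of the Investigator".

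**Module 1 table (protocol 5.2.8, Table 4).** For a first Grade 3-4 event: "resume at the next lowest dose level when resolved". For Grade below 3: "Resume at same dose prior to interruption". The row headed "Grade 3-4 toxicity (subsequent events" (diarrhoea excluded) requires permanent discontinuation.

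**Evaluability in Module 3 (protocol 5.4.4; SAP VI.J.5).** A patient is evaluable with the full Cycle 0 dose and at least 80% of the intended dose in Cycles 1 and 2, or by the alternative route: "Has permanently discontinued study treatment due to a related adverse event". Each arm needs six evaluable patients.

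**The concern.** The text makes lack of clinical benefit a reason to stop that is separate from whether the event has resolved. The tables, in the rows for general toxicity, make resolution the trigger for resuming. A site that reads one passage and not the other can act correctly by the protocol and still do the opposite of what the other passage says.

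Two things are at stake. The first is patient safety and consistent management: the same patient may be stopped or re-exposed. The second is the make-up of the Module 3 evaluable set. Permanent discontinuation for a related event makes a patient evaluable. Resumption after a long hold can leave the patient short of 80% and outside the six. Module 3 exists to show whether intermittent schedules are tolerated, so this affects the patients it is meant to inform about.

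**Working it through.** No hypothesis is tested and the plan gives no figure to reproduce. The check sets the passages side by side and then counts doses.

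**1. Clinical benefit as a condition.** Take a related Grade 3 event that resolves on day 10 of a hold, in a patient with no clinical benefit.

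| Source | Benefit needed to restart? | Instruction |
|---|---|---|
| 5.4.6 | Yes | Discontinue |
| Table 7, first Grade 3-4 row | No (hold is 14 days or less) | Resume one level down |
| 5.2.7 | Yes, if this is one of the undefined other events | Discontinue |
| Table 4, first Grade 3-4 row | No (hold is 14 days or less) | Resume one level down |

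The Grade below 3 row of Table 4 also has no benefit condition. Elsewhere the tables do add conditions. The β-CTX rows of both tables and the corticosteroid row of Table 4 use clinical benefit, and the Grade 2 and 3 colitis rows of Table 7 require a steroid taper. Because the tables name benefit where they want it, its absence from the Grade 3-4 row cannot simply be filled in from the text.

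**2. Sponsor agreement.** 5.2.7 and 5.4.6 require it for a restart after resolution. The Grade 3-4 rows require Sponsor consultation only beyond 14 days (Table 4 asterisk, Table 7 footnote b).

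**3. A further Grade 3-4 event at the lowest dose (Module 1 only).** A 1.0 mg patient has a Grade 3 event, is reduced to 0.5 mg (the Cohort 1 dose) and has another Grade 3 event. Table 4 stops the patient permanently. The lowest-dose sentence in 5.2.7 sets no limit on grade or number of events, so it permits a restart at the Investigator's discretion.

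**4. Effect on Module 3 evaluability.** Inputs: 21-day cycles; Arm 1 doses 4 days in 7; Arm 2 doses 14 days in 21 (5.4.4); maximum hold 14 days (Table 7); threshold 80%.

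- Arm 1 intended doses in Cycles 1-2: 4 × 6 weeks = 24. Any 14 consecutive days contain 8 dosing days. Remaining: 24 − 8 = 16, and 16/24 = 67%.
- Arm 2 intended doses: 14 × 2 = 28. A 14-day hold contains between 0 and 7 scheduled off-days, so it loses between 14 and 7 doses. Remaining: 14/28 = 50% to 21/28 = 75%.

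All are below 80%. For shorter holds the boundary is:

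- Arm 1: 20/24 = 83% with four doses lost, 19/24 = 79% with five.
- Arm 2: 23/28 = 82% with five doses lost, 22/28 = 79% with six.

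These are counts of dosing days. In milligrams against a fixed 2 mg, the share is lower still once dosing resumes at a reduced level. Only if the held doses are themselves valued at the reduced level can the share exceed the day count. With an assumed 1.5 mg level and a hold from C2D8 to C2D21, it is (21 × 2)/(21 × 2 + 7 × 1.5) = 42/52.5 = 80%, which just meets the threshold. The protocol does not say which convention applies.

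**The case against.** The best answer is that the text adds a condition on which the tables are silent, so a careful reader applies both. In addition, the Sponsor physician must agree to an ordinary restart, which limits divergence between sites, and Table 7 separately lets the Investigator stop for any clinically significant event. The agreement requirement does reduce the risk. It does not remove it, because the table row itself asks for consultation only beyond 14 days and no passage gives the text precedence.

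Several stronger readings are tempting and are not supported:

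- *That 5.2.7 generally allows restart after a second Grade 3-4 event.* It never mentions one, and its general restart is tied to the rules that follow, which lead to Table 4. The conflict arises only for a patient already reduced to the Cohort 1 dose. The sentence may have been meant to fill a gap, since no lower level exists there.
- *That the tables resume on resolution alone throughout.* The β-CTX, corticosteroid, colitis and over-14-day provisions add conditions.
- *That benefit cannot be judged before the first scan at week 6 ± 1.* The tables elsewhere treat benefit as the Investigator's assessment, and Section 7.1 allows unscheduled scans. What is missing from 5.4.6 is who judges benefit and how.
- *That one patient moves a planned discontinuation rate by 1 in 6.* SAP Section IX uses the Safety Population, meaning everyone dosed, and tabulates withdrawals, reductions and interruptions separately. The patient stays in the denominator; only the category of action changes.

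It is also unstated whether a patient whose event has resolved, and who stops for lack of benefit, has discontinued because of a related adverse event. If not, that patient may be unevaluable as well.

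**Conclusion.** The contradiction stands for 5.4.6 against the first Grade 3-4 row of Table 7. It also stands for 5.2.7 against the first Grade 3-4 and Grade below 3 rows of Table 4, subject there to the undefined scope phrase. The lowest-dose conflict is real but narrow. Protocol Section 5.4 describes Module 1 as complete and SAP Section I refers to its database lock, so Module 3 is where the point still matters.

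In size, this is a wording fault with a safety bearing and a limited analysis effect. It can change who is re-treated and, after a full 14-day hold counted in dosing days, who is among the six evaluable patients. The contrast between a stopped patient who counts and a re-treated patient who does not assumes that the stop is classed as due to a related adverse event. How often the situation would arise cannot be worked out from the documents: the median Module 1 exposure of about 7 weeks says nothing specific about Grade 3-4 events that resolve.

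**What to change.** Reconcile 5.4.6 with Table 7, and 5.2.7 with Table 4 for consistency, so that text and table state identical restart conditions:

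- whether clinical benefit is required, and if so who judges it and how;
- whether Sponsor physician agreement is needed for every restart or only beyond 14 days;
- which events the discontinuation sentence in 5.2.7 covers;
- what happens after a further Grade 3-4 event in a patient already at the lowest dose.

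In 5.4.4 and SAP Section VI.J.5, state whether a stop for lack of benefit after an event counts as discontinuation due to a related adverse event, and whether the 80% is measured against the original or the reduced dose. Which clinical rule applies is for the sponsor's clinicians. The cost is a protocol wording change and a matching line in the SAP, with no new data or patients.
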